7.5.1.1. Reporting SAEs to Pfizer Safety

All SAEs occurring in a patient during the active collection period as described above in Section 7.5.1 are reported to Pfizer Safety on the CT SAE Report Form immediately upon awareness and under no circumstance should this exceed 24 hours, as indicated in Appendix 4. The investigator will submit any updated SAE data to the sponsor within 24 hours of it being available.

If a patient begins a new anticancer therapy, SAEs occurring during the above-indicated active collection period must still be reported to Pfizer Safety irrespective of any intervening treatment. Note that a switch to a commercially available version of the study treatment is considered as a new anticancer therapy for the purposes of SAE reporting.

7.5.1.2. Recording Nonserious AEs and SAEs on the CRF

All nonserious AEs and SAEs occurring in a patient during the active collection period, which begins after obtaining informed consent as described in Section 7.5.1, will be recorded on the AE section of the CRF.

The investigator is to record on the CRF all directly observed and all spontaneously reported AEs and SAEs reported by the patient.

If a patient begins a new anticancer therapy, the recording period for nonserious AEs ends at the time the new treatment is started; however, SAEs must continue to be recorded on the CRF during the above-indicated active collection period. Note that a switch to a commercially available version of the study treatment is considered as a new anticancer therapy for the purposes of SAE reporting.

7.5.2. Method of Detecting AEs and SAEs

The method of recording, evaluating, and assessing causality of AEs and SAEs and the procedures for completing and transmitting SAE reports are provided in Appendix 4.

Care will be taken not to introduce bias when detecting AEs and/or SAEs. Open-ended and nonleading verbal questioning of the patient is the preferred method to inquire about AE occurrences.

7.5.3. Follow-up of AEs and SAEs

After the initial AE/SAE report, the investigator is required to proactively follow each patient at subsequent visits/contacts. For each event, the investigator must pursue and obtain adequate information until resolution, stabilization, the event is otherwise explained, or the patient is lost to follow-up (as defined in Section 6.11).

In general, follow-up information will include a description of the event in sufficient detail to allow for a complete medical assessment of the case and independent determination of possible causality. Any information relevant to the event, such as concomitant medications and illnesses, must be provided. In the case of a patient death, a summary of available autopsy findings must be submitted as soon as possible to Pfizer Safety.

Further information on follow-up procedures is given in Appendix 4.

7.5.4. Regulatory Reporting Requirements for SAEs

Prompt notification by the investigator to the sponsor of an SAE is essential so that legal obligations and ethical responsibilities towards the safety of patients and the safety of a study treatment under clinical investigation are met.

The sponsor has a legal responsibility to notify both the local regulatory authority and other regulatory agencies about the safety of a study treatment under clinical investigation. The sponsor will comply with country-specific regulatory requirements relating to safety reporting to the regulatory authority, IRBs/ECs, and investigators.

Investigator safety reports must be prepared for SUSARs according to local regulatory requirements and sponsor policy and forwarded to investigators as necessary.

An investigator who receives SUSARs or other specific safety information (eg, summary or listing of SAEs) from the sponsor will review and then file it along with the Investigator Brochures for the study and will notify the IRB/EC, if appropriate according to local requirements.

7.5.5. Exposure During Pregnancy or Breastfeeding, and Occupational Exposure

Exposure to the study treatment under study during pregnancy or breastfeeding and occupational exposure are reportable to Pfizer Safety within 24 hours of investigator awareness.

7.5.5.1. Exposure During Pregnancy

An EDP occurs if:

- A female patient is found to be pregnant while receiving or after discontinuing study treatment.
- A male patient who is receiving or has discontinued study treatment exposes a female partner prior to or around the time of conception
- A female is found to be pregnant while being exposed or having been exposed to study treatment due to environmental exposure. Below are examples of environmental exposure during pregnancy:
 - A female family member or healthcare provider reports that she is pregnant after having been exposed to the study treatment by ingestion.
 - A male family member or healthcare provider who has been exposed to the study treatment by ingestion then exposes his female partner prior to or around the time of conception.

The investigator must report EDP to Pfizer Safety within 24 hours of the investigator's awareness, irrespective of whether an SAE has occurred. The initial information submitted should include the anticipated date of delivery (see below for information related to termination of pregnancy).

- If EDP occurs in a patient or a patient's partner, the investigator must report this information to Pfizer Safety on the CT SAE Report Form and an EDP Supplemental Form, regardless of whether an SAE has occurred. Details of the pregnancy will be collected after the start of study treatment and until 6 months after the last dose.
- If EDP occurs in the setting of environmental exposure, the investigator must report information to Pfizer Safety using the CT SAE Report Form and EDP Supplemental Form. Since the exposure information does not pertain to the patient enrolled in the study, the information is not recorded on a CRF; however, a copy of the completed CT SAE Report Form is maintained in the investigator site file.

Follow-up is conducted to obtain general information on the pregnancy and its outcome for all EDP reports with an unknown outcome. The investigator will follow the pregnancy until completion (or until pregnancy termination) and notify Pfizer Safety of the outcome as a follow-up to the initial EDP Supplemental Form. In the case of a live birth, the structural integrity of the neonate can be assessed at the time of birth. In the event of a termination, the reason(s) for terminated be specified and, if clinically possible, the structural integrity of the terminated fetus should be assessed by gross visual inspection (unless preprocedure test findings are conclusive for a congenital anomaly and the findings are reported). Abnormal pregnancy outcomes are considered SAEs. If the outcome of the pregnancy meets the criteria for an SAE (ie, ectopic pregnancy, spontaneous abortion, intrauterine fetal demise, neonatal death, or congenital anomaly), the investigator should follow the procedures for reporting SAEs. Additional information about pregnancy outcomes that are reported to Pfizer Safety as SAEs follows:

- Spontaneous abortion including miscarriage and missed abortion;
- Neonatal deaths that occur within 1 month of birth should be reported, without regard to causality, as SAEs. In addition, infant deaths after 1 month should be reported as SAEs when the investigator assesses the infant death as related or possibly related to exposure to the study treatment.

Additional information regarding the EDP may be requested by the sponsor. Further followup of birth outcomes will be handled on a case by case basis (eg, followup on preterm infants to identify developmental delays). In the case of paternal exposure, the investigator will provide the patient with the Pregnant Partner Release of Information Form to deliver to his partner. The investigator must document in the source documents that the patient was given the Pregnant Partner Release of Information Form to provide to his partner.

7.5.5.2. Exposure During Breastfeeding

An exposure during breastfeeding occurs if:

- A female patient is found to be breastfeeding while receiving or after discontinuing study treatment.
- A female is found to be breastfeeding while being exposed or having been exposed to study treatment (ie, environmental exposure). An example of environmental exposure during breastfeeding is a female family member or healthcare provider who reports that she is breastfeeding after having been exposed to the study treatment by inhalation or skin contact.

The investigator must report exposure during breastfeeding to Pfizer Safety within 24 hours of the investigator's awareness, irrespective of whether an SAE has occurred. The information must be reported using the CT SAE Report Form. When exposure during breastfeeding occurs in the setting of environmental exposure, the exposure information does not pertain to the patient enrolled in the study, so the information is not recorded on a CRF. However, a copy of the completed CT SAE Report Form is maintained in the investigator site file.

An exposure during breastfeeding report is not created when a Pfizer drug specifically approved for use in breastfeeding women (eg, vitamins) is administered in accord with authorized use. However, if the infant experiences an SAE associated with such a drug, the SAE is reported together with the exposure during breastfeeding.

7.5.5.3. Occupational Exposure

An occupational exposure occurs when a person receives unplanned direct contact with the study treatment, which may or may not lead to the occurrence of an AE. Such persons may include healthcare providers, family members, and other roles that are involved in the trial patient's care.

The investigator must report occupational exposure to Pfizer Safety within 24 hours of the investigator's awareness, regardless of whether there is an associated SAE. The information must be reported using the CT SAE Report Form. Since the information does not pertain to a patient enrolled in the study, the information is not recorded on a CRF; however, a copy of the completed CT SAE Report Form is maintained in the investigator site file.

7.5.6. Cardiovascular and Death Events

Not applicable

7.5.7. Disease-Related Events and/or Disease-Related Outcomes Not Qualifying as AEs or SAEs

Not applicable.

7.5.8. Adverse Events of Special Interest

See Section 2.1.4 Clinical Safety of Combination Encorafenib and Binimetinib for descriptions of AESIs.

All AESIs must be reported as an AE or SAE following the procedures described in Section 7.5.1 through Section 7.5.1.2. An AESI is to be recorded as an AE or SAE on the CRF. In addition, an AESI that is also an SAE must be reported using the CT SAE Report Form.

7.5.8.1. Lack of Efficacy

Lack of efficacy is reportable to Pfizer Safety only if associated with an SAE.

7.5.9. Medical Device Deficiencies

Not applicable.

7.5.10. Medication Errors

Medication errors may result from the administration or consumption of the study treatment by the wrong patient, or at the wrong time, or at the wrong dosage strength.

Exposures to the study treatment under study may occur in clinical trial settings, such as medication errors.

| Safety Event | Recorded on the AE CRF | Reported on the CT SAE Report Form to Pfizer Safety Within 24 Hours of Awareness |
|-------------------|--------------------------------------|---|
| Medication errors | Only if associated with an AE or SAE | Only if associated with an SAE |

Medication errors include:

- Medication errors involving patient exposure to the study treatment;
- Potential medication errors or uses outside of what is foreseen in the protocol that do or do not involve the study patient.

In the event of a medication dosing error, the sponsor should be notified within 24 hours.

If applicable, any associated AE(s), serious and nonserious, are recorded on the AE page of the CRF.

Medication errors should be reported to Pfizer Safety within 24 hours on a CT SAE Report Form **only when associated with an SAE**.

7.6. Treatment of Overdose

There is no antidote known to over dosage either encorafenib or binimetinib. Supportive measures should be instituted.

In the event of an overdose, the investigator/treating physician should:

- 1. Contact the medical monitor within 24 hours.
- 2. Closely monitor the patient for any AEs/SAEs and laboratory abnormalities for at least 5 half-lives or 28 calendar days after the overdose of study treatment (whichever is longer). Closely monitor the patient for any AEs/SAEs.
- 3. Document the quantity of the excess dose as well as the duration of the overdose in the CRF.
- 4. Overdose is reportable to Safety only when associated with an SAE.

Decisions regarding dose interruptions or modifications will be made by the Investigator in consultation with the Sponsor Medical Monitor based on the clinical evaluation of the patient.

The Sponsor collects product complaints on study treatments used in clinical studies in order to ensure the safety of study patients, monitor quality, and facilitate process and product improvements.

All product complaints associated with material packaged, labeled, and released by the Sponsor (or designee) will be reported to the Sponsor. All product complaints associated with other study material will be reported directly to the respective manufacturer.

The Investigator or his/her designee is responsible for reporting a complete description of the product complaint via email or other written communication to the Sponsor contact or respective manufacturer as noted in the packaging information. Any AE associated with a product complaint should be recorded as described in Section 7.5.1.1.

If the Investigator is asked to return the product for investigation, he/she will return a copy of the product complaint communication with the product.

7.8. Pharmacokinetics

For patients enrolled under Protocol Versions 0 through 3, serial blood samples (~4 mL each) for plasma PK analysis of encorafenib, its metabolite (LHY746), and binimetinib will be collected as shown in Table 12.

For patients enrolled under Protocol Version 4 or later, blood samples (~4 mL each)for plasma concentration of encorafenib, its metabolite (LHY746), and binimetinib will be collected as shown in Table 13.

Complete instructions for sample processing, handling and shipment will be provided in the Laboratory Manual.

Study visits for PK sampling should be scheduled in the morning so that proper predose and postdose PK blood samples can be collected. On the PK visit days, the morning doses of encorafenib and binimetinib will be taken at the study site under observation by the Investigator or designee at approximately the same time, only after collecting the predose PK sample. Predose sampling information will include the date and exact time of the most recent previous dose of binimetinib and encorafenib (except Cycle 1 Day 1), including the dose amount taken. Postdose sampling information, only needed for days with postdose PK sampling (i.e., Cycle 1 Day 1 and Cycle 1 Day 15), will include the date and exact time of the morning dose, including the dose amount taken. Except for the Cycle 1 Day 1 PK samples, which have to be obtained on the scheduled day, other PK samples may be obtained ± 1 day from the scheduled date.

If vomiting occurs within 4 hours following study treatment administration on the day of PK sampling, no additional study treatment will be taken in an effort to replace the material that has been vomited and it is recommended that no more PK samples be taken after the emesis occurs. Any vomiting that occurs will be noted in the PK eCRF. Further doses will be administered with premedication with antiemetic medications and PK sampling will be performed after premedication with antiemetics.

In addition, exploratory analyses on remaining plasma samples may be performed using a validated or non-validated, semi-quantitative or qualitative liquid chromatography tandem mass spectrometry method, if deemed appropriate.

Table 12.Serial Pharmacokinetic Blood Sample Timing in Patients Enrolled under
Protocol Versions 0 through 3

| Study Visit | Timing of Sample |
|----------------|---|
| Cycle 1 Day 1 | 0.5 hours (± 5 min) post dose 1.5 hours (± 5 min) post dose 3 hours (± 10 min) post dose 6 hours (± 20 min) post dose |
| Cycle 1 Day 15 | Predose (within 30 minutes prior to dose) 0.5 hours (± 5 min) post dose 1.5 hours (± 5 min) post dose 3 hours (± 10 min) post dose 6 hours (± 20 min) post dose |
| Cycle 2 Day 1 | • Predose (within 30 minutes prior to dose) |

Table 13.Pharmacokinetic Blood Sample Timing in Patients Enrolled under
Protocol Version 4 or later

| Study Visit | Timing of Sample |
|---------------|---|
| Cycle 1 Day 1 | • Predose (within 30 minutes prior to dose) |
| Cycle 2 Day 1 | • Predose (within 30 minutes prior to dose) |
| Cycle 3 Day 1 | • Predose (within 30 minutes prior to dose) |
| Cycle 4 Day 1 | • Predose (within 30 minutes prior to dose) |
| Cycle 5 Day 1 | • Predose (within 30 minutes prior to dose) |
| Cycle 6 Day 1 | • Predose (within 30 minutes prior to dose) |

7.9. Pharmacodynamics

Pharmacodynamic parameters are not evaluated in this study.

7.10. Biomarkers

Patients will be eligible for the study based on identification of a $BRAF^{V600}$ mutation in the tumor or blood as determined by the local laboratory, and are required to also submit archival or fresh tissue to confirm $BRAF^{V600}$ mutation status by a central laboratory (see

If the patient consents, and in accordance with local laws, any tumor (archival or fresh) or blood samples remaining after determination of *BRAF*-mutation status may be stored for up to 5 years (or according to local regulations) after the completion of the study. Research will focus on biomarkers relevant to *BRAF* V600-mutant cancer. Potential future testing of DNA, RNA and protein from the biomarker samples, for example, may include somatic mutation molecular analyses (i.e., PCR) and IHC assays. No cell lines or model systems will be generated from the samples. All samples and data collected in connection with the study will be encoded by the study doctor and patient identity for all samples will remain unknown to others, including the study Sponsor. Raw data will not be shared and will not be uploaded to public databases. Summarized data may be shared as part of a collaborative research projects for publications. The decision to perform such exploratory biomarker research studies would be based on outcome data from this study or from new scientific findings related to the drug class or disease, as well as reagent and assay availability. The Sponsor will be the exclusive owner of any data and discoveries resulting from this study. Genetic testing results can be provided at the completion of the study upon request.

7.10.1. Circulating Tumor DNA Biomarker Analysis

provided in the Laboratory Manual.

In addition to the supplied tumor biopsy sample, blood samples will be collected as outlined in the SoA (see Table 3). The blood samples will be processed to plasma and purified ctDNA analyzed for potential genomic markers of encorafenib and/or binimetinib activity. The blood samples may be used for companion diagnostics or for exploratory research investigating genetic variants in ctDNA, such as $BRAF^{V600}$ mutations as well as additional tumor mutations.

The biomarker samples should be drawn prior to PK samples. Complete instructions for sample collection, processing, handling and shipment to a central laboratory will be provided in the Laboratory Manual.

Further exploratory biomarker research may be conducted on collected blood (including PK) samples. These additional investigations would be dependent upon clinical outcome, reagent and sample availability.

Samples may be stored for up to 5 years (or according to local regulations) following completion of the study to enable further analysis of biomarker responses to encorafenib and binimetinib.

7.10.2. Circulating Serum Biomarker Analysis

After IRB/IEC approval of Protocol Version 4 or later, peripheral blood samples (serum) will be collected as specified in the SoA (Table 3) for analysis of potential proteomic or metabolomic factors and signals.

7.11. Genetics

See Section 7.10.

7.12. Patient-Reported Outcomes

Patient-reported outcomes are not evaluated in this study.

7.13. Health Economics

Health Economics or Medical Resource Utilization and Health Economics parameters are not evaluated in this study.

8. STATISTICAL CONSIDERATIONS

A detailed SAP will be prepared by the Sponsor or designee. This plan may modify the statistical methods outlined in the protocol; however, any major modifications of the primary endpoint definition or analysis will also be described in a protocol amendment.

8.1. Statistical Hypotheses

The primary endpoint of the study is ORR for treatment-naïve and previously treated patients as determined by IRR per RECIST v1.1. The study is designed to test the null hypothesis of ORR \leq 39% for treatment- naïve patients with *BRAF*^{V600E} NSCLC, which is considered not sufficiently clinically meaningful to warrant further study in this indication where similar therapies are already available. The alternative hypothesis is ORR >39% with the assumption that the true ORR is at least 65%. Hypotheses are based on the results observed in the dabrafenib plus trametinib study in *BRAF*^{V600E}-mutant NSCLC patients, in which the ORR per Investigator assessment was 64% (95% CI: 46, 79) for treatment-naïve patients (Planchard et al, 2017) and the results observed in patients with NSCLC whose tumors expressed PD-L1 levels with a TPS \geq 50% and received pembrolizumab as a single agent (Keynote-042) in which ORR per IRR was 39% (95% CI: 34, 45) (Mok et al, 2019).

For previously treated patients with $BRAF^{V600E}$ NSCLC, the null hypothesis of ORR $\leq 20\%$ will be tested. The alternative hypothesis is ORR $\geq 20\%$ with the assumption that the true ORR is at least 45%. This hypothesis is based on the ORR of 18% (95% CI: 14, 23) observed in previously treated patients with NSCLC whose tumors expressed PD-L1 levels with a TPS $\geq 1\%$ and who received pembrolizumab as a single agent (Keynote-010; Herbst et al, 2016).

8.2. Sample Size Determination

The sample size calculation is based on the primary endpoint of ORR as determined by IRR per RECIST v1.1. The hypotheses to be tested are described in Section 8.1. With 60 evaluable treatment-naïve patients with $BRAF^{V600E}$ NSCLC, the power is greater than 95% to test the null hypothesis that the ORR is less than or equal to 39% versus the alternative hypothesis that it is greater than 39% assuming an alternative target rate of 65% with a one-sided $\alpha \le 0.025$ based on a single-stage design using exact test. The null hypothesis will be rejected if ≥ 32 confirmed objective responses are observed. With 37 evaluable previously treated patients with $BRAF^{V600E}$ NSCLC, there is at least 90% power to test the null hypothesis that the ORR is less than or equal to 20% versus the alternative hypothesis that it is greater than 20% assuming an alternative target rate of 45% with a one-sided $\alpha \le 0.025$ based on a single stage design using exact test. The null hypothesis that it is greater than 20% assuming an alternative target rate of 45% with a one-sided $\alpha \le 0.025$ based on a single stage design using exact test. The null hypothesis that it is greater than 20% assuming an alternative target rate of 45% with a one-sided $\alpha \le 0.025$ based on a single stage design using exact test. The null hypothesis will be rejected if ≥ 13 confirmed objective responses are observed.
At least 60 treatment-naïve and 37 previously treated $BRAF^{V600E}$ NSCLC patients will be enrolled and treated. It is not expected that more than 107 patients with any $BRAF^{V600}$ mutation will be enrolled and treated.

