4. STUDY DESIGN

4.1. Overall Design

This is an open-label, multicenter, non-randomized, Phase 2 study to determine the safety, tolerability and efficacy of encorafenib given in combination with binimetinib in treatment-naïve and previously treated patients with $BRAF^{V600E}$ -mutant metastatic NSCLC. Although very rare in NSCLC, patients with other V600 Class 1 *BRAF* mutations (e.g., K or D) are also allowed. Patients who are either treatment-naïve, OR who have received 1) first-line treatment with standard platinum-based chemotherapy, OR 2) first-line treatment with an anti-PD-1/PD-L1 inhibitor given alone, or in combination with platinum-based chemotherapy, or in combination with immunotherapy (e.g., ipilimumab) with or without platinum-based chemotherapy will be enrolled. Treatment will be administered in 28-day (\pm 3 days) cycles and will continue until the patient meets the protocol-defined criteria for treatment withdrawal (see Section 6.7). Once the patient discontinues study treatment, the treatment period will end, and the patient will enter the follow-up period for safety, subsequent anticancer therapy, disease status, and survival status (see Section 7.1.4).

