6.10. Enrollment of Additional Patients

Additional patients may be enrolled to ensure that there are at least 60 treatment-naïve patients and 37 previously treated patients whose tumors have locally confirmed $BRAF^{V600E}$ mutation, and who have received at least one dose of study treatment. Up to 10 additional patients who have a $BRAF^{V600}$ mutation other than $BRAF^{V600E}$ ($BRAF^{V600x}$) can be enrolled and treated. It is not expected that more than 107 patients with any $BRAF^{V600}$ mutation will be enrolled and treated.

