8.4.1. Primary Analyses

The primary endpoint is ORR in treatment-naïve and previously treated patients with $BRAF^{V600E}$. It is defined as the proportion of patients who have achieved a confirmed best overall response of CR or PR as determined by IRR per RECIST v1.1, relative to the SS.

The ORR will be calculated with an exact two-sided 95% CI.

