4.3. Sample Size Considerations

The sample size calculation is based on the primary endpoint of ORR as determined by IRR per RECIST v1.1. The hypotheses to be tested are described in [Section 4.2](#).

At least 60 treatment-naïve and 37 previously treated $BRAF^{V600E}$ NSCLC participants will be enrolled and treated. It is not expected that more than 107 participants with any $BRAF^{V600}$ mutation will be enrolled and treated.

With 60 evaluable treatment-naïve participants with $BRAF^{V600E}$ NSCLC, the power is greater than 95% to test the null hypothesis that the ORR $\leq 39\%$ versus the alternative hypothesis that it is $> 39\%$ assuming an alternative target rate of 65% with a one-sided $\alpha \leq 0.025$ based on a single-stage design using exact test. The null hypothesis will be rejected if ≥ 32 confirmed objective responses are observed out of 60 participants.

With 37 evaluable previously treated participants with $BRAF^{V600E}$ NSCLC, there is at least 90% power to test the null hypothesis that the ORR $\leq 20\%$ versus the alternative hypothesis that it is $> 20\%$ assuming an alternative target rate of 45% with a one-sided $\alpha \leq 0.025$ based on a single stage design using exact test. The null hypothesis will be rejected if ≥ 13 confirmed objective responses are observed out of 37 participants.

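### Do the fixed response counts (32 of 60, 13 of 37) leave the primary decision open if a cohort enrols more than planned?

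*Protocol*

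**What the plan says.** Protocol 8.1 and SAP 4.2 set the null response rates by independent radiology review: at most 39% in treatment-naïve and at most 20% in previously treated participants with BRAF V600E disease. Protocol 8.2 names the test (exact, single stage, one-sided alpha of at most 0.025) and, for 60 and 37 evaluable patients, gives the rejection counts. The previously treated null is rejected when at least "13 confirmed objective responses are observed". That clause has no denominator of its own. SAP 4.3 repeats both rules and supplies one: at least "32 confirmed objective responses are observed out of 60 participants" and at least "13 confirmed objective responses are observed out of 37 participants".

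Enrolment is a minimum. Protocol 6.10 says "Additional patients may be enrolled to ensure that there are at least 60" treatment-naïve and 37 previously treated patients with the V600E mutation. The overall ceiling is soft; Protocol 8.2 says "It is not expected that more than 107 patients with any" V600 mutation. Protocol 8.4.1 defines the primary rate "as determined by IRR per RECIST v1.1, relative to the SS", that is, over the Safety Set, so every treated V600E patient in a cohort is counted. For analysis, Protocol 8.4.1 and SAP 7.5.1 plan the rate with an exact two-sided 95% interval (Clopper-Pearson in the SAP). Neither section compares the lower limit with 39% or 20%.

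**The concern.** A count is valid only for the sample size it was derived for. Here the sample size may exceed the planned number, nobody is dropped to bring the denominator back to 60 or 37, and the protocol clause read alone gives a bare count. The analysis sections do not repeat the test.

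Overshoot is possible within the plan. The ceiling of 107 is 60 + 37 + 10, where the 10 are optional places for other V600 mutations. Protocol 4.1 describes these as uncommon: "Although very rare in NSCLC, patients with other V600 Class 1" BRAF mutations are also allowed. If those places do not fill, either V600E cohort can grow without passing 107.

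At stake are the two primary hypotheses of a study that was amended (Protocol Appendix 9, Version 4) to support registration. If the count were kept in a larger cohort, a boundary result could be declared a success while its own 95% interval still included the null rate.

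**Working it through.** **Inputs.** Null rates 39% and 20% (Protocol 8.1, SAP 4.2); target rates 65% and 45%, sizes 60 and 37, counts 32 and 13, exact test, one-sided alpha ≤ 0.025 (Protocol 8.2, SAP 4.3).

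**Formulas.** For n patients and cut-off r, alpha = P(X ≥ r) with X binomial(n, null rate); power is the same tail at the target rate. The Clopper-Pearson lower limit for x responses in n is the 2.5% quantile of Beta(x, n − x + 1).

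**Step 1: reproduce the plan.**
- Naïve, 32 of 60: alpha 0.0170, power 97.7%. With 31 of 60, alpha would be 0.0313.
- Previously treated, 13 of 37: alpha 0.0231, power 91.6%. With 12 of 37, alpha would be 0.0517.

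Both counts are the smallest that meet 0.025, and the stated powers (above 95%, at least 90%) hold.

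**Step 2: room for overshoot under 107.** 60 + 38 = 98 leaves 107 − 98 = 9 places for other mutations; 62 + 37 = 99 leaves 107 − 99 = 8.

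**Step 3: count carried over, against the test the plan names.**

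| Cohort | n | Alpha with planned count | Lower limit at planned count | Exact-test cut-off | Alpha at that cut-off | Lower limit at that cut-off |
|---|---|---|---|---|---|---|
| Previously treated (13) | 37 | 0.0231 | 20.2% | 13 | 0.0231 | 20.2% |
| Previously treated (13) | 38 | 0.0288 | 19.6% | 14 | 0.0120 | 21.8% |
| Naïve (32) | 60 | 0.0170 | 40.0% | 32 | 0.0170 | 40.0% |
| Naïve (32) | 61 | 0.0226 | 39.3% | 32 | 0.0226 | 39.3% |
| Naïve (32) | 62 | 0.0295 | 38.6% | 33 | 0.0161 | 40.1% |

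The extremes under 107, with no other mutations enrolled and all extra patients in one cohort, are 107 − 37 = 70 naïve (alpha 0.1518 if 32 were kept) and 107 − 60 = 47 previously treated (0.1306 if 13 were kept).

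**Step 4: how many results change.** At 38, only exactly 13 responses: 0.0288 − 0.0120 = 0.0168 probability at a true rate of 20%. At 62, only exactly 32: 0.0295 − 0.0161 = 0.0134 at 39%. At the target rates the same results have probability 0.054 (45%) and 0.010 (65%).

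**Step 5: does the planned interval give the same decision?** The Clopper-Pearson lower limit is the rate at which P(X ≥ x) equals 0.025, and that tail rises with the rate. The limit therefore lies above the null rate exactly when the tail at the null rate is below 0.025, which is the named test. Direct calculation agrees: both rules gave the same minimum count for every n from 20 to 119 under both nulls. Across the nearest sizes the counts are 32 at n = 60–61, 33 at n = 62–63, 13 at n = 37 and 14 at n = 38–41.

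**The case for a change.** The case for a change is that the test and alpha stand only in sample-size text premised on 60 and 37, while the analysis sections promise an interval and no decision. An analyst holding the protocol clause alone could apply 13 to 38 patients; one holding the named test would require 14. A study meant to support registration should settle that before results are known, and one sentence would do it.

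Part of this stands. The analysis sections do not restate the rule, overshoot is permitted, and the arithmetic in Step 3 is right. The conclusion does not follow. A null rate, an exact test and an alpha limit determine the rejection region at any sample size, so what is missing is a restatement and not a rule. Nothing in either document directs anyone to carry a count to another denominator. The SAP is the later document (26 May 2022, against 24 September 2021 for Protocol Version 5). Protocol 8 says of it: "This plan may modify the statistical methods outlined in the protocol". Major changes to the primary analysis would need an amendment, but attaching 60 and 37 to the counts only spells out the protocol's own premise. Using 13 at 38 would mean disregarding both the SAP's denominator and the alpha limit stated with the test.

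**Conclusion.** No change is needed. The plan is correct at its planned sizes and determines the decision at any other size through the named exact test. Type I error would exceed 0.025 only through misapplication. That takes an overshoot of at least one previously treated or two naïve patients, a count kept against the SAP's denominators and the stated alpha, and, at those smallest overshoots, a result exactly on the boundary (probability 0.0168 or 0.0134 at the null rates). The reported interval would then show the conflict, since its lower limit would be 19.6% or 38.6%.

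This rests on two assumptions: that the analysis follows the test and alpha stated in Protocol 8.2 and SAP 4.3, and that the cohort size used is the number of treated V600E patients. The documents do not give the realised sizes, and the conclusion does not depend on them. Writing the interval-based rule into the analysis sections would be an optional editorial courtesy, equivalent to what is already specified.
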